Attachment B. Invite scripts for Treatment Engagement Incentive Study

Discuss the purpose of of the call

Hi, I am specialist X X from your healthcare provider, GHC- SCW, and I've called as part of an important benefit to our patients to help them quit smoking.

Let me please confirm whom I'm speaking with. [CONFIRMS CALLER IS MEMBER OF GHC-SCW.] We want to make sure all our patients who smoke know about the many ways we can help them with their smoking. Quitting smoking is the best thing you can do for your health, but quitting can be hard. We are here to help even if you are not ready to quit yet."

First, can you confirm your date of birth? Check against EHR to make sure you have the correct patient on the phone.

"I see your last your last visit with us was in Y Y."

- Ask the patient "Are you still smoking?"

If patient initially responds they are no longer smoking, ask "So, just to confirm, you have not had even one puff over the last seven days?"

If 0, click "No" (Informational Alert should trigger with reminder to adjust Smoking Status in Vital Signs/Social History. Congratulate the patient on quitting and thank them for taking the call. If you need support contact us at xxx-xxx-xxxx.

If >0, click "Yes" advise them to quit and offer treatment: "The most important thing you can do to improve your health is to quit smoking and I can help you. I can help provide medications, and treatment support over the phone and via text messages.

Also, check against EHR that patient:

- a) Is on the Cigarette User Registry for a participating clinic
- b) Does not have an existing target quit date ±30 days from date of call to TCOS
- c) Current billable insurance documented as other than Medicare or non-BadgerCare Medicaid
- d) Preferred language is either English or Spanish

If either a, b, c, or d, is untrue→ offer tobacco use treatment or resources as per usual standard care.

IF a, b, c, & d, true→ Continue

RANDOMIZE

Randomized to \$0 incentive

"As a GHC-SCW member, you may be eligible for a special study that may include receiving money for participating in treatment for those willing to make an attempt to quit smoking in the next 30 days. If you are interested, let's discuss getting you started now. Is this something you are interested in?"

Randomized to either \$100, or \$50 incentive

"As a GHC-SCW member, you may be eligible for \$[XX] to make an attempt to quit smoking in the next 30 days. You would receive ½ of it for completing your first telephone counseling session and the rest for completing the Week 4 counseling session. If you are interested, let's discuss getting you started now. Is this something you are interested in?"

Are you interested in trying to quit smoking in the next 30 days?

N/A (I DON'T SMOKE) YES NO

NO → *Thanks, we understand that it's not always the right time to quit. OK. Would you like my direct line or the number of the Wisconsin Tobacco Quit Line? YES NO*

YES → *I can be reached 8-4 at xxx-xxxx, the quit line toll free number is: [[name]]. Their staff are available 7 days a week, 24 hours a day.*

NO → *Thank you for your time.*

YES → *We'd like to ask you to be in a research study to help us figure out the best ways of offering this support. We at GHC-SCW and our research partners at the University of Wisconsin, or UW-Madison are trying to find ways to help smokers quit right now. If you're interested in the study, we can see if you qualify for it. If you don't qualify, or you aren't interested in the study, we still have support to offer you to quit. I can help you now or you can talk to your doctor or call the Wisconsin Tobacco Quit Line for phone coaching and 2 weeks of free nicotine replacement medication. Would you like to hear more about the study now? This will take 2 minutes.*

YES NO

GO TO TREATMENT ENGAGEMENT INCENTIVE STUDY CONSENT PROCESS.

NO → *Thanks, we understand that that this may not be the right fit. Would you like my direct line or the number of the Wisconsin Tobacco Quit Line? YES NO*

YES → *I can be reached 8-4 at xxx-xxxx, the quit line toll free number is: [[name]]. Their staff are available 7 days a week, 24 hours a day. [confirm mailing address for Contact Incentive]*

NO → *Thank you for your time. [confirm mailing address for Contact Incentive]*

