4.0 Goals/Aims

4.1 Goals This project will apply a three-armed randomized block design to identify whether financial incentives are effective in increasing acceptance of, and engagement in, smoking intervention services as well as smoking cessation amongst Group Health Cooperative (GHC-SCW) patients who smoke. All members of the GHC-SCW Cigarette Users Registry (i.e., individuals who the health system believes are smokers, the 'Registry') at the time of implementation will be eligible to participate. Smokers who speak with the TCOS staff when called for standard care management outreach following a recent primary care visit or during an annual outreach call and listen to the description of smoking treatments will be randomized to receive one of three incentive amounts (\$0, \$100, & \$50) for continuing treatment planning, establishing a target quit date and completing two telephone counseling sessions. Participants will be told about the size of their incentive, which in theory will increase their likelihood of engaging in smoking treatment and therefore, quitting smoking successfully. For the non-\$0 incentive groups, ½ the total value will be apportioned for completion of each a Pre-quit

counseling call and a Week 4 counseling call. Participants (N=540) will be recruited in up to 6 primary care clinics with randomization blocked on clinic so that roughly 1/3 of all enrollees in a given clinic will be in each of the treatment use incentive conditions to avoid incentive by clinic confounds. Sex and minority status will also be used as blocking factors to limit confounding the impact of the incentive on these demographic characteristics.

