6.0 Subject Selection

6.1 Subject Identification

Up to 540 adult participants will be recruited from the 6 primary care clinics of the GHC-SCW healthcare system over 6-12 months. All patients who meet criteria for the existing GHC-SCW Cigarette Use Registry who do not have an existing Target Quit Date \pm 30 days and who either are currently contacted by the TCOS following each primary care encounter or are identified as not having had a primary care encounter in prior 365 days. During this outreach TCOS will provide the incentive offer and recruit for participation. GHC-SCW also currently provides quarterly bulk communications promoting the availability of tobacco use treatment through their TCOS. Patients who initiate contact with a TCOS in response to these messages will also be offered enrollment. TCOS are healthcare system employees nationally certified in tobacco treatment and will have completed all relevant human subjects research, HIPAA, and good clinical practice trainings to enable them to become members of the study team for the performance of screening, consenting, randomization, phone-based assessments, and other research activities, as required. Patients can participate in the incentive research program only once but can use the GHC-SCW standard smoking treatment program repeatedly.

The TCOS will explain that the healthcare system is reaching out to all smokers to offer support and resources to help them protect their health. The TCOS will trigger the randomization assignment, advise all patients who smoke to quit, let them know that s/he can offer help in quitting, and ask if patients are interested in quitting within the next 30 days. If the patient is assigned to either the \$100 or \$50 incentive, the TCOS will inform the patient that they can earn that incentive for setting a quit plan within the next 30 days and completing two smoking treatment counseling calls. If patients are in the \$0 incentive condition they will be offered the opportunity to enter the smoking cessation treatment program with no offer of a financial incentive for treatment engagement, which is consistent with usual care. If patients agree to receive smoking treatment, they will be asked brief screening questions.

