In addition to the engagement incentives, \$20 for completing a telephone survey 6 months after their original Target Quit Date and \$50 in compensation will be offered to patients for completing the 6-month post-enrollment visit for biochemical validation of abstinence from smoking. This payment for completing this important research assessment will be available to all enrolled participants, regardless of assigned experimental condition.

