For these reasons, we also propose to use an altered HIPAA authorization because it would be impracticable to obtain authorization with all elements required under the HIPAA Privacy Rule over the phone. We also seek to waive some of the required elements of consent and HIPAA authorization over the phone in order to reduce participant burden and to enhance comprehension of the material read to participants, without omitting any key information pertinent to risks, rights, or protections. Consent and HIPAA authorization over the phone will cover the collection of data from the electronic health record for research purposes. The mailed Study Information Sheet that will follow the telephone enrollment and oral consent process will include all required elements of consent and HIPAA authorization (including a statement regarding how long permission to use the PHI will last, how to withdraw permission for PHI use, and the mandatory statement that the PHI could be redisclosed without subjects' permission in the consent/authorization and enrollment process). The Study Information Sheet also details how to withdraw from the study and revoke authorization to use PHI, without penalty or punishment. The mailed Study Information Sheet will provide a phone number for participants to call should they have questions.

The TCOS will ask if the participant gives the study permission to stay in touch with them and send them reminders about upcoming study contacts during the study via email and/or text message. The TCOS will remind them that email and text messaging are generally not a secure way to communicate about their health as there are many ways for unauthorized users to access email and text messages. The TCOS will also inform them that they do not have to provide their email address or text message number to participate in this study.

With regard to compensation and incentives, the Consent Script and mailed Study Information Sheet will make clear distinctions between compensation for completing the 6-month follow-up assessment and smoking abstinence biochemical confirmation (available in all conditions), and incentives for treatment engagement (available to about 2/3 of participants). This is important for

the sake of transparency and to ensure that incentive effects are not masked by misattribution of compensation as an incentive by participants.

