6.5 Randomization

Randomization will occur during the contact call immediately after patients have been told of their smoking treatment options. The TCOS will then use randomization tables developed by UW-CTRI to randomize potential enrollees, blocked by clinic, sex, and race, into 1 of 3 engagement incentive conditions (\$0, \$100, or \$50). After randomization, patients will be offered smoking treatment with the incentive for treatment entry (engagement) to which they had been randomized. This offer will require the participant to agree to set a stop-smoking quit date within the next 30 days. This offer will occur prior to the patient's provision of consent to participate in research. The patient must be offered the incentive up-front to see if this increases their treatment engagement (which necessarily includes agreement to it/consent); offering the incentive after agreeing to participate in treatment would not reveal the effects of the incentive on spurring engagement. Thus, we are interested in the effects of incentives on both agreement to enter treatment and actual likelihood of engaging in it. If a patient decides to accept the treatment offer, s/he will be consented and will set a target quit date with the TCOS (within 1 month of the contact phone call). For patients who are unwilling to set a stop-smoking quit date within the next 30 days the TCOS will describe all stop-smoking treatment options that are available as part of usual care and encourage the patient to call the TCOS back when ready to set a quit date within 30 days. For patients who decline the research study, the TCOS will describe all stop-smoking treatment options that are available as part of usual care and provide quit smoking treatment as usual.

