8.0 Detailed Study Procedures: Recruitment and Assessments

8.1 Recruitment As noted in the enrollment flow diagram in Attachment A, recruitment will occur over the phone (in the Treatment Planning call) following a patient response to standard TCOS outreach. TCOS as per their current GHC-SCW usual care protocol will provide callers with advice to quit and an overview of cessation treatment options. The TCOS will assess the smoker's readiness to quit in the next 30 days as per usual care. In accordance with randomized condition, the TCOS will offer the appropriate intervention incentive per the Invite Script (Attachment B). For those who tell the TCOS that they are ready to quit within 30 days, the TCOS will offer treatment enrollment and provide standard care per the existing tobacco treatment program of the GHC-SCW healthcare system (e.g., setting quit date, arranging timing of treatment contacts: See Figure 2.).

The TCOS will be trained to present information about the Treatment Engagement Incentive offer, assessing eligibility, informed consent, and research assessment processes in a standardized manner.

UW-CTRI personnel will be responsible for: conducting telephone follow-up interviews 3- and 6-months post-TQD and meeting with patients to verify claimed abstinence 6-months post-TQD via biochemical testing (breath CO, urine, and/or saliva testing without biobanking). The

Figure 2. GHC-SCW Healthcare System Standard Tobacco Treatment Program

All patients on the Cigarette Users Registry receive:

- Quarterly Bulk Outreach via postal mail and MyChart promoting the tobacco treatment program services
- Care Management telephonic outreach calls by TCOS following each primary care visit and no less than once per year.

Patients are offered ongoing access to resources but expected to set a target quit date (TQD) to focus cessation planning and arrange medications. Elements include:

- 3 brief telephone counseling sessions with a Certified Tobacco Treatment Specialist (TCOS)
 - 3-5 days pre-,
 - 5-7 days post- (Week 1),
 - 4 weeks post-TQD (Week 4)
- Smoking cessation pharmacotherapy including combination NRT, varenicline, or any of 7 FDA approved medications.
- Integrated referrals to:
 - primary care physician
 - WI Tobacco Quit Line
 - SmokefreeTXT program
- Weekly facilitated Tobacco Use Support Group
- Ongoing TCOS support through MyChart (EHR patient portal) and phone

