9.3 Planned Analysis

Primary Aim

- To determine the relations between treatment engagement financial incentive amounts offered and likelihood of patient engagement in smoking cessation treatment (defined as setting a TQD and completing the two phone counseling calls (Pre-quit + Week 4).

Primary analysis. The primary outcome measure will be patient engagement in smoking cessation treatment (defined as setting a TQD and the number of completed phone counseling contacts). We will determine the percentage of those in each incentive condition who engage in smoking cessation treatment. We will use logistic regression analyses to contrast the likelihood of engaging in any smoking treatment (vs none) for the three incentive conditions (0 incentive, \$100, and \$50), with the 0 incentive condition being the reference condition in the primary analysis. We will also examine incentive condition effects on the number of scheduled counseling visits completed (0-3 visits) via ordinal logistic regression.

Additional exploratory analyses related to the primary aim. In additional exploratory analyses, we will determine the percentage of all GHC patients who are contacted by the TCOS and offered the Treatment Engagement Incentive. We will separately determine the percentage of those in each incentive condition who agree to set a TQD. We will use logistic regression analyses to contrast the likelihood of engaging in smoking treatment for the three incentive conditions, with (as mentioned above) the 0 incentive condition being the reference condition in the primary analysis, followed by comparison of the \$100 and \$50 conditions both with the reference condition and with one another. The primary analyses will not use covariates. Follow-up analyses will use the patient's home clinic and the patient's TCOS as covariates. Furthermore, using logistic regression, we will examine the relation between incentive condition and use of pharmacotherapy as the outcome (with medication orders and pick-up entered in the EHR and/or billing data).

Exploratory Aims

- Conduct exploratory analyses on the effects of the different incentive engagement amounts on biochemically confirmed point-prevalence 6-month abstinence and determine whether incentive conditions affect abstinence via their effects on smoking treatment engagement (i.e., whether smoking treatment engagement mediates the relations between different engagement incentive conditions and 6-month smoking abstinence).

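### Section 6.1 defines the $0 reference arm as receiving no incentive offer, but its invitation script raises possible payment for treatment; the two must be reconciled

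*Combined protocol and SAP*

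**What the plan says.** Section 6.1 describes what patients assigned to $0 are given on the outreach call: an invitation to the cessation program "with no offer of a financial incentive for treatment engagement, which is consistent with usual care".

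Attachment B gives the words to be spoken. After the eligibility check and the randomization step, a patient assigned to $0 hears: "you may be eligible for a special study that may include receiving money for participating in treatment". A patient assigned to $50 or $100 instead hears the amount, and that half is paid for each of two counseling calls.

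Section 8.1 makes the attachment the delivered text: "the TCOS will offer the appropriate intervention incentive per the Invite Script (Attachment B". Section 6.4 also describes the study offer as tailored to the assigned value and cites the same attachment.

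Section 9.3 contrasts the three conditions by logistic regression "with the 0 incentive condition being the reference condition in the primary analysis".

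**The concern.** The two texts describe the same arm at the same moment and do not agree. One says that arm is offered no incentive. The other tells it that payment for taking part in treatment is possible.

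The moment matters. Section 6.5 explains why the amount is revealed before consent: "The patient must be offered the incentive up-front to see if this increases their treatment engagement". The invitation is therefore part of the experimental manipulation, and what the reference arm hears there is part of the definition of the control.

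The protocol recognises a related risk. Section 6.4 wants assessment payments and engagement incentives kept apart "to ensure that incentive effects are not masked by misattribution of compensation as an incentive by participants". It places that safeguard in the consent script and the mailed information sheet, and both come after the invitation.

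At stake is the meaning of the primary contrast: whether $50 and $100 are compared with no mention of an incentive, or with an open-ended possibility of one.

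**Working it through.** No planned figure is in dispute. The check sets the texts side by side and adds one small count.

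1. **Same arm, same step.** Section 6.5 gives the order as randomization, then the offer, then consent. Attachment B follows it: eligibility check, randomization, arm-specific opening, question about quitting within 30 days, then the study invitation and consent. Section 6.1 describes that same opening. Both texts are current.

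2. **Can the $0 arm earn money for treatment?** Section 4.1 says that, for the non-$0 groups, half "the total value will be apportioned for completion of each a Pre-quit" call and a Week 4 call. Per arm:
   - $0: nothing is apportioned, so $0.
   - $50: 50 / 2 = $25 per call; 2 × 25 = $50.
   - $100: 100 / 2 = $50 per call; 2 × 50 = $100.

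   Section 6.4 agrees: engagement incentives are open to about two thirds of participants, which is 2 of 3 equal arms.

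3. **Do the payments open to all arms explain the phrase?** Sections 6.3, 6.4 and 8.2 provide $20 for the 6-month telephone survey and $50 "for completing the 6-month post-enrollment visit for biochemical validation of abstinence from smoking". Both pay for research assessments. The script ties the money to taking part in treatment, so they do not explain it.

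4. **What differs between the openings.**

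| Element | $0 script | $50/$100 script |
|---|---|---|
| Lead-in | a special study | the amount |
| Money | possible, unspecified, for treatment | stated amount, half per call |
| Request | quit attempt within 30 days | quit attempt within 30 days |

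   All arms hear about the research study later, in common wording. The openings therefore differ in more than whether an incentive is offered.

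5. **Which comparisons are touched.** Three arms give 3 pairwise contrasts. Two ($50 v $0, $100 v $0) use the $0 arm, and these are the two for which section 9.4 sizes the trial. The third ($100 v $50) does not use it.

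6. **Effect on engagement.** The documents give no figure for how the phrase changes acceptance, quit-date setting or call completion, so no size is computed.

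**The case against.** The best defence is that a non-specific mention of money was intended. The synopsis calls the design active placebo-controlled. Section 5.0 says research participants will be told they may receive an engagement incentive. Section 6.4 has consent mention possible payments while withholding the amounts, to avoid refusals from disappointment. The $0 script is also doubly conditional and names no sum, so 6.1 could be read loosely as meaning no specific offer.

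Much of this stands: the text to change may well be 6.1 rather than the script. It does not remove the conflict. The synopsis label is unexplained, section 5.0 describes people in the study, and section 6.4 describes consent. None addresses the $0 invitation or qualifies 6.1. A possible payment for treatment is neither no offer nor shown to be usual care.

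The invitation is also only an early step. Engagement under section 9.3 requires a quit date plus the Pre-quit and Week 4 calls, and section 6.4 has the $50 and $100 groups reminded of their incentive. The reviewed text describes the consent script but does not reproduce it in full, so later wording might clarify the $0 position. That is a fair limit on how much weight one sentence can carry.

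Three stronger readings are tempting, and the documents support none of them.

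- A reader might infer that the phrase raises control engagement, shrinks the contrast and costs power. That is plausible, but the special-study lead-in or later disappointment could act the other way, and no size is given.
- A reader might infer that the 15% control rate in section 9.4 assumes a control told nothing of money. That section credits outreach-specialist contact and the chance to set a quit date; its silence about payment does not show what wording was assumed.
- A reader might infer that results will be reported against usual care. Sections 9.3 and 9.4 speak of a zero-incentive condition, and the cost analysis takes usual care to be the program before the study.

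**Conclusion.** The inconsistency is established from the text. The $0 arm is defined in 6.1 as receiving no incentive offer, while its operative script raises possible payment for treatment that the arm cannot earn. If the script is followed, the primary contrasts at the invitation compare a stated amount with a possible, unspecified payment.

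In extent, this touches both comparisons with control and leaves $100 versus $50 alone. Its effect on engagement is unknown in direction and size, and the point does not rest on any assumed shift.

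It does rest on two assumptions: that Attachment B is spoken as written, as section 8.1 requires, and that nothing said before the invitation changes its meaning. The documents do not settle whether 6.1 or the script states the intended control, so the point is a request to reconcile them. It should be acted on because it concerns the definition of the reference arm and the remedy is cheap.

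**What to change.** Reconcile section 6.1 with Attachment B and state which control is intended.

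- **(a) If a no-offer control is intended:** reword the $0 script as a complete invitation to treatment and a quit attempt within 30 days, without the money phrase or the special-study lead-in. Leave the study and the assessment payments to the wording common to all arms. Simply deleting the money from the $50/$100 opening will not do, because that opening is built around the amount. Cost: a script amendment and IRB notification, and consent in the $0 arm may fall.
- **(b) If the wording is deliberate or already in use:** correct the no-offer and usual-care descriptions in 6.1. State in the primary analysis and the conclusions that the control heard of a possible, unspecified payment. Cost: corrected text only.

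If the script changes during the trial, record the version used on each call and report results by version, noting that version is confounded with calendar time.
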